### 9.4. ANALYSIS SETS

The following data sets will be used for the statistical analysis:

1. **Safety Set:** All randomized subjects who received at least one dose of double-blind study drug irrespective of the treatment received. Subjects will be analyzed according to treatment received.
2. **Full Analysis Set (FAS):** All randomized subjects who received at least one dose of double-blind study drug irrespective of the treatment received. Subjects will be analyzed according to randomized treatment.
3. **Week 12 Per Protocol (PP) Set:** All subjects in the FAS excluding those identified as major protocol violators up to Week 12.
4. **Week 24 Per Protocol (PP) Set:** All subjects in the FAS excluding those identified as major protocol violators up to Week 24.
5. **Pharmacokinetic (PK) Set:** all subjects who received active study medication and had no major protocol deviations.

Any pre-planned sub-group analyses will be described in the statistical analysis plan (SAP).

### 9.5. DATA ANALYSIS

More details of the proposed statistical analysis will be documented in the SAP, which will be written following finalization of the protocol and prior to the interim analysis of the Part A data.

Analyses of Part B study data will be fully described in the SAP.

For continuous data and for ordered categorical data, if appropriate, the number of non-missing observations, mean, standard deviation, median, first and third quartiles, minimum and maximum will be calculated.

For ordered categorical data and nominal data, absolute counts and relative frequencies (in %) will be calculated.

Data for the 75mg group and 75mg titrated group will be combined for the analyses of the Part A data.

All statistical hypothesis tests and confidence intervals will be two sided, using a type I error rate of 0.05. No adjustment for multiple comparisons will be used for this study.

Raw data will be listed.

### **9.5.1. Baseline Assessment**

Descriptive statistics will be performed on relevant screening and baseline data (i.e. data collected prior to the treatment administration) and on demographic characteristics for each treatment group and overall. There will be no formal comparison of baseline data, that is, no statistical hypothesis testing.

### **9.5.2. Primary Efficacy Analysis**

Mean overall pelvic pain scores will be calculated separately for the VRS and NRS by adding up the daily pain scores during each successive 4-week (28 day) periods and dividing by the actual number of days with non missing data (i.e. nominally 28 days if no missing data). The baseline mean overall pelvic pain score will be calculated as the mean over the two complete menstrual cycles during screening, which may not be exactly 28 days each.

The percentage of subjects with a 30% or greater reduction from baseline to week 12 (i.e. during the 4 weeks preceding week 12 time point) in the mean overall pelvic pain score will be summarized by descriptive statistics for each treatment group and overall.

The analysis of the primary endpoint will be conducted via a generalized linear model for binary data with repeated (correlated) measures, fitted using generalized estimating equations (a marginal model), with the model including terms for treatment group, 4-week period, baseline and the interactions 4-week period\*treatment, 4-week period\*baseline.

### **9.5.3. Secondary Efficacy Analysis**

Mean overall pelvic pain scores will also be calculated separately for the NRS in the same way as for the VRS.

Mean pelvic pain scores on uterine bleeding days and non-uterine bleeding days will be calculated by adding up the pain scores on the relevant days (uterine bleeding days will be defined as those days on which the subject records any uterine bleeding or spotting in the subject eDiary) and dividing by the number of days with non missing data. Both the total number of non-missing days in the 4-week period (i.e. nominally 28 days if no missing data) and the number of non-missing uterine bleeding days/non-uterine bleeding days will be considered.

All secondary efficacy endpoints will be summarized by descriptive statistics for each treatment group and overall, for each time point, including summaries or change from baseline when applicable. The definition of baseline for each endpoint will be defined in the SAP. As with the primary analysis, individual active versus placebo arm comparisons will be made. In addition, an overall test for dose response will be conducted using all treatment arms.

In general, between group comparisons for continuous endpoints will be analyzed via (repeated measures) analysis of (co)-variance (repeated measures mixed models) or Wilcoxon Rank Sum tests, subject to the underlying distribution of the data. Between group comparisons for binary endpoints will be analyzed via generalized linear models (with repeated measures) and chi-squared tests. Between-group comparisons for count data (e.g. number of days) will also be analyzed via generalized linear models (with repeated measures).

It is not certain whether the continuous endpoints will be normally or log-normally distributed, and/or whether an absolute or proportional change in endpoints will be observed. If deemed necessary, the data will be log transformed prior to the analysis. The subsequent results (mean differences and corresponding confidence intervals) will be back transformed and hence reported in terms of ratios of geometric means.

Potential responder definitions for future studies will be explored. These are likely to incorporate use of rescue analgesics and reduction in difficulty of pain with daily activities, in addition to pain. A responder threshold that constitutes a meaningful reduction in symptomatology will also be explored, potentially by exploring a cumulative distribution and/or via an anchor based method using the PGIC and other appropriate endpoints and methods.

#### **9.5.4. Safety analysis methodology**

The safety and tolerability profile will be assessed versus baseline conditions and differences between treatment groups and descriptive statistics will be produced, where applicable. No formal hypothesis testing of safety data will be undertaken.

A treatment-emergent analysis will be done for AEs. AEs will be tabulated by MedDRA preferred term and system organ class. Tabulations by severity and drug-relatedness will also be made.

Extent of exposure and compliance will be evaluated.

The Safety Analysis Set shall be used when summarizing safety data.

#### **9.5.5. Pharmacokinetic analysis methodology**

PK Analysis will be performed by SGS Laboratories. The analyses have to be performed unblinded by the analytical laboratory. The analyst may be aware of the subject number, sampling time and dose group. For descriptive statistics of plasma concentrations mean (arithmetic and geometric), standard deviation, median, 1st and 3rd quartiles, minimum, maximum, coefficient of variation (CV%) and number of observations will be provided. Concentrations below the limit of quantification (LOQ) will be assigned a value of zero.

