### 3.3. PHARMACOKINETIC-PHARMACODYNAMIC ENDPOINTS

- Plasma levels of OBE2109 and its metabolite KP017 measured pre-dose and 1.5–2hrs post-dose on Day 1, pre-dose at weeks 4 and 16 visits, and post-dose at weeks 8, 12, 20 and 24 visits.

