## 4. STUDY DESIGN

This is a prospective, dose-finding, randomized, parallel group, double-blind, placebo-controlled phase 2b study investigating the efficacy and safety of OBE2109 in the treatment of women with endometriosis-associated pain.

The study duration (from the Screening visit to the End-of-Study visit) will be up to 64 weeks per subject.

[figure not shown]
The study starts with an 11±5 week screening period evaluating the endometriosis pain over at least two full, spontaneous menstrual cycles. During this period, the subject will receive no study drug.

Eligibility will be confirmed on Day 1 based on data collected during the screening period. On Day 1, subject will be randomized to one of 6 treatment groups: placebo, fixed-dose groups at 50, 75, 100 and 200 mg daily and a titrated-dose group. After randomization, a 24-week active treatment period, composed of 2 periods of 12 weeks each (Part A and Part B), and a subsequent 24-week treatment-free period will follow.

A schematic of the study design is shown in Figure 1.

Figure 1: Study design

In the placebo group, the placebo will be provided for 12 weeks (Part A) after which all placebo subjects will be crossed-over on to active treatment (100 mg daily) for a further 12 weeks (Part B).

In the titrated-dose arm, all subjects will start on 75 mg daily for 12 weeks (Part A) after which the dose will be titrated up or down to 100 or 50 mg, or remain at the same dose for the following 12 weeks (Part B). Up- or down-titration will depend on the mean of serum E2 assay results collected at weeks 4 and 8. Serum E2 levels will not be communicated to the investigational and the sponsor study teams to maintain the blind. Possible up- or down- titration will occur according to the following algorithm: subjects with a mean serum E2 level of <20pg/mL will be down-titrated to 50 mg daily whereas subjects with a mean serum E2 level of >50 pg/mL will be up-titrated to 100 mg daily. Subjects with a mean serum E2 level from 20 to 50 pg/mL inclusive will remain on 75 mg daily. Mean serum E2 level will be defined as the mean of the serum E2 assay results collected at week 4 and week 8.

An Interactive Web Response System (IWRS) will be used to allocate the appropriate treatment.

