#### **6.5. OBE2109 AND KP017 PLASMA LEVELS**

PK blood samples will be collected from each subject for determining OBE2109 and KP017 plasma levels.

On Day 1, blood samples for PK assessment will be taken pre-first dose and 1.5 to 2 h post-first dose.

On the day of the site visits of weeks 8, 12, 20 and 24, the subject will take her daily dose of IMP at home at the usual time in the morning. The blood samples for PK will be taken at the site. The time of

dose administration in the morning and time of PK sampling on the same day will be recorded on the eCRF.

On weeks 4 and 16 visits, the subject will be asked to take the dose of IMP at site, after a pre-dose PK sampling. The time of dose administration on the previous day and time of taking of the PK sample will be recorded on the eCRF.

Details of blood sampling process, sample handling and shipment are described separately in a laboratory manual provided by the central laboratory.

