### 9.2. SAMPLE SIZE

The planned sample size for this study is 55 subjects per treatment arm (330 subjects in total). The sample size calculation is based on pairwise comparisons for each active dose versus placebo. A two-sided type I error of 0.05, not adjusted for multiple comparisons against placebo, will be used for this exploratory study. Fifty five (55) subjects per arm will provide a power of 90% assuming a placebo response rate of 45.5% and an active treatment response rate of 76.9% (based on data from Kissei's Phase 2 study KLH1202).

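### Values below LOQ are set to zero while geometric means are reported, so one such value makes that cell's geometric mean 0 or undefined (minor; PK descriptive tables only)

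*Combined protocol and SAP*

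**What the plan says.** Section 9.5.5 (Pharmacokinetic analysis methodology) sets the summaries: "For descriptive statistics of plasma concentrations mean (arithmetic and geometric), standard deviation, median, 1st and 3rd quartiles", followed by minimum, maximum, CV% and number of observations. The next sentence reads: "Concentrations below the limit of quantification (LOQ) will be assigned a value of zero". The synopsis, under Data Analysis and Statistics, carries the same pair of instructions.

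Neither place limits the zero rule to particular statistics. There is no substitution or exclusion rule for log-scale summaries, no rule for leaving a statistic uncalculated, and no request for the number of values below LOQ. Section 9.5.7 (Missing Data) does not deal with values below LOQ.

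The PK endpoint in section 3.3 begins with "Plasma levels of OBE2109 and its metabolite KP017 measured pre-dose and 1.5–2hrs post-dose on Day 1" and goes on to pre-dose samples at weeks 4 and 16 and post-dose samples at weeks 8, 12, 20 and 24. Section 6.5 confirms that on Day 1 "blood samples for PK assessment will be taken pre-first dose and 1.5 to 2 h post-first dose". Section 9.4 defines the PK Set as "all subjects who received active study medication and had no major protocol deviations".

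Section 9.5 leaves further analysis detail to a SAP to be written before the Part A interim analysis. No SAP text in the supplied document alters the zero rule.

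**The concern.** A geometric mean is computed through logarithms, and zero has none. Two adjacent sentences therefore ask for a statistic and fix its inputs so that the statistic fails in any cell holding one value below LOQ. The resulting entry carries no information about the other values in the cell, however many there are.

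What is at stake is the readability of the exposure tables in a dose-ranging trial, where plasma level is the only listed PK endpoint. An affected cell would show a geometric mean of 0 or a blank. Otherwise the programmer would have to choose a handling rule that the plan does not contain, possibly after the unblinded Part A data are available.

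**Working it through.** The plan gives no figure to reproduce, so the check uses the definition, an illustration and the sampling schedule.

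**Inputs from the protocol**
- Zero rule and geometric mean: section 9.5.5 and the synopsis.
- Cell size: 55 per arm (section 9.2). In Part A the two 75 mg arms are combined (section 9.5), giving up to 2 × 55 = 110.
- Half-life about 15–20 hours (section 1.5.1), with once-daily dosing.
- Week 24 procedures for women who discontinue between Day 1 and Week 24 (section 6.7.2). These include a PK sample labelled post-dose (section 6.2.3.2).

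**Inputs assumed** (the document gives no LOQ and no concentrations)
- 54 quantifiable values at evenly spaced log-normal quantiles, geometric mean 1000, CV 50%, plus one value below LOQ.
- LOQ of 1, 5 or 10 in the same units.
- Per-sample probability of a value below LOQ: 0.5%, 1%, 2% or 5%.

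**Step 1: definition.** GM = (x1 × … × xn)^(1/n) = exp(mean of ln x). If any x = 0, the product is 0 and GM = 0. On the log form, ln 0 = −∞ and GM is undefined.

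**Step 2: effect of one zero in a cell of 55**

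| Statistic | 54 quantifiable values | With one zero added (n = 55) |
|---|---|---|
| Geometric mean | 1000 | 0 (mean of logs −∞) |
| Arithmetic mean | 1115 | 1115 × 54/55 ≈ 1094 |
| Median | 1000 | 989 |

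If LOQ/2 replaces the zero, GM = exp[(54 × ln 1000 + ln(LOQ/2))/55]:
- LOQ 1: 871
- LOQ 5: 897
- LOQ 10: 908

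If only quantifiable values are used and the count below LOQ is reported, GM = 1000.

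**Step 3: chance that a cell holds at least one such value**, 1 − (1 − p)^n

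| p | n = 55 | n = 110 |
|---|---|---|
| 0.5% | 24% | 42% |
| 1% | 42% | 67% |
| 2% | 67% | 89% |
| 5% | 94% | 99.6% |

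**Step 4: where such values can arise**
- *Day 1 pre-dose.* The sample precedes the first dose, and recent GnRH antagonists and experimental drugs are excluded (section 5.2.2). The whole cell should be below LOQ, so GM is 0 or undefined and CV% is 0/0. No dose comparison depends on this cell.
- *Placebo arm, Part A.* These women receive 100 mg in Part B (section 4), so they can enter the PK Set. If their Part A samples are tabulated, that column behaves like Day 1 pre-dose.
- *On treatment, dosing as planned.* The fraction left after 24 h is 0.5^(24/15) = 0.33 to 0.5^(24/20) = 0.44. Few values below LOQ would be expected.
- *Early discontinuation.* One week is 168 h, which is 168/20 = 8.4 to 168/15 = 11.2 half-lives. The fraction left is 0.5^8.4 ≈ 0.3% down to 0.5^11.2 ≈ 0.04%. A sample taken then under the Week 24 procedures could fall below LOQ. If it is tabulated at Week 24, it sets that cell's geometric mean to zero.

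**The case against.** The strongest reply is that little follows from the conflict. The one near-certain case, Day 1 pre-dose, is a cell where zero is the right description. With a half-life of 15–20 hours, women who take their tablets should rarely be below LOQ, and excluding major deviations from the PK Set may remove some who do not. The same table gives the arithmetic mean, median, quartiles and n, so a geometric mean of 0 beside a median near 1000 would be seen as an artefact. Detail is deferred to a SAP. These points stand, and they set the severity. They do not remove the conflict. The zero rule is written without exception in two places, and the document does not say whether discontinuation samples are kept out of the Week 24 cell.

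Four stronger readings are tempting, and the document does not support them:
- *The metabolite is likely to be below LOQ.* No LOQ, concentration or half-life is given for KP017, and section 1.4.1 calls it the main metabolite.
- *The exposure-response work is compromised.* Section 9.5.6 describes graphs and statistical modelling. It does not say that zeros or cell geometric means enter them.
- *The two rules cannot both be applied.* On the product form they can, but the answer is an uninformative 0.
- *Software will silently drop the zeros.* No software is named.

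**Conclusion.** The point holds as a minor one. As written, section 9.5.5 and the synopsis give a geometric mean of 0 or undefined in any cell with at least one value below LOQ. In the assumed cell of 55, a single such value takes the geometric mean from 1000 to 0, while the arithmetic mean falls by about 2% (1115 to 1094).

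That a zero destroys the geometric mean follows from its definition and needs no assumption. The illustrative concentrations, the LOQ range and the per-sample probabilities in the working are assumed. How many on-treatment cells would be affected cannot be determined from the document; it shows only that some could be.

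The consequence is limited to the PK descriptive tables. The hypotheses in section 9.1, the sample size in section 9.2 and the primary analysis in section 9.5.2 do not use PK summaries.

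**What to change.** Add one sentence to section 9.5.5 and to the synopsis, and carry it into the SAP before the Part A interim analysis:

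- Keep zero for arithmetic statistics, and state that the zero rule does not apply to geometric means.
- For geometric means, name one log-scale rule in advance, for example LOQ/2 or quantifiable values only. Either is an accepted convention.
- Report the number of values below LOQ in each cell.
- Show the geometric mean as not calculated where most or all values are below LOQ, as at Day 1 pre-dose.

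The change needs no new data. It puts a second handling rule in the same table, and the result depends somewhat on the convention chosen: in the illustration, 871–908 with LOQ/2 against 1000 with quantifiable values only. Reporting the count below LOQ lets a reader judge that dependence.

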#### **9.5.6. Pharmacodynamic analysis methodology**

Possible PK-PD relationships will be investigated graphically and through statistical modeling, whilst also exploring possible covariates.

#### **9.5.7. Missing Data**

Summary statistics will be based primarily on non-missing values. For hypothesis tests, estimates and confidence intervals, missing values for continuous efficacy endpoints analyzed via likelihood methods (e.g. repeated measures mixed models) will not be directly imputed as they are handled within the analysis itself, under the assumption that the model specification is correct and that the data is missing at random. In addition, missing values for endpoints analyzed via generalized estimating equations will not be directly imputed as they are handled under the assumption that the model specification is correct and the data is missing completely at random. Sensitivity analyses may be conducted to check the

robustness of the analysis results under alternative assumptions with regards to missing data. Further details on the handling of missing values, including rules applied to incomplete questionnaires (including incomplete diary entries) and any planned sensitivity analyses will be defined in the SAP.

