Summary statistics will be based primarily on non-missing values. For hypothesis tests, estimates and confidence intervals, missing values for continuous efficacy endpoints analyzed via likelihood methods (e.g. repeated measures mixed models) will not be directly imputed as they are handled within the analysis itself, under the assumption that the model specification is correct and that the data is missing at random. In addition, missing values for endpoints analyzed via generalized estimating equations will not be directly imputed as they are handled under the assumption that the model specification is correct and the data is missing completely at random. Sensitivity analyses may be conducted to check the robustness of the analysis results under alternative assumptions with regards to missing data.

Further details on the handling of missing values, including the rules applied to incomplete questionnaires (including incomplete diary entries) and any planned sensitivity analyses will be defined in the Statistical Analysis Plan.

o Interim analysis

After all subjects have completed the first 12-week period (Part A), an interim analysis of Part A data to assess the efficacy and safety parameters will be performed. The OBE2109 75mg group and OBE2109 75mg titrated group will be pooled for the analysis of the Part A data.

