**6.7.2. Subject Withdrawal from Study**

Subjects will be informed that they have the right to withdraw from the study at any time, without prejudice to their medical care, and that they are not obliged to state the reason(s). Any withdrawal must be fully documented in the eCRF exit form and should be followed up by the Investigator.

The Investigator may withdraw a subject at any time if this is considered to be in the subject's best interest.

In addition, the sponsor could make a decision to temporarily or permanently discontinue the study for safety, ethical, compliance or other reasons. In this case, the subject's participation may be ended prematurely without asking for her consent.

Subjects discontinuing participation in the study between Day 1 and Week 24 visits should undergo the procedures required at Week 24 visit. Subjects discontinuing participation in the study between Week 24 and Week 36 visits should undergo the procedures required at Week 36 and Week 48 visits. Subjects discontinuing participation in the study between Week 36 and Week 48 visits should undergo the procedures required at Week 48 visit.

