**6.7.2.1. Discontinuation criteria**

During the course of the study, the subject may be discontinued for the following reasons:

- **Lack of Efficacy:** Investigator's judgment only. If subject's opinion only, check subject's Request. Explain in the comment section of the eCRF Exit Form.
- **Adverse Event:** Includes clinically significant new or worsening existing condition as judged by the Investigator. Document in the AE form.
- **Subject's Request:** Consent withdrawal, subject moved, schedule conflicts, etc. Specify the reason in the comment section of the eCRF Exit Form.
- **Protocol Violation:** Major protocol violation which may affect the subject's safety. Specify the protocol violation in the comment section of the eCRF Exit Form.
- **Lost to Follow-up:** Document with two phone calls and a certified letter requesting return receipt without response. Document in the comment section of the eCRF Exit Form.
- **Pregnancy:** Subjects that have been exposed to study treatment and who become pregnant during the treatment period will be immediately withdrawn from treatment. Pregnancies that have been exposed to study treatment and occurred up to week 36, or started up to 4 weeks after treatment discontinuation in case of early withdrawal will be followed up for pregnancy and neonatal outcomes at birth. Any pregnancy must be reported with the Pregnancy Surveillance Form (see section 8.6).
- **Other:** Specify in the Comments section in the eCRF Exit Form. This reason should only be used if the reason for discontinuation is not better accounted for by another category.

Subjects who have an elevation of hepatic enzymes suspicious of drug induced liver toxicity according to the Food and Drug Administration (FDA) guidance on drug-induced liver injury (26), i.e. LFT increase > 3 x ULN associated with increased bilirubin > 1 x ULN, will be immediately withdrawn from treatment and followed up to return to normal of hepatic parameters.

All subjects withdrawn from treatment will enter – if appropriate – a 24-week follow-up period without treatment and continue daily eDiary recording up to Week 36 visit in order to continue to collect efficacy data.

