**6.7.2.2. Follow-up for discontinued subjects**

Not applicable.

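### The primary week-12 responder analysis imputes nothing and assumes data missing completely at random, although women may stop for lack of efficacy; a missing-at-random method costs little

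*Combined protocol and SAP*

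**What the plan says.** Section 3.1.1 defines the primary endpoint as a reduction of at least 30% from baseline in the 4-week mean VRS pelvic pain score at week 12. Section 9.5.2 analyses it as repeated binary data by GEE, with treatment, period, baseline and two interactions. It names no working correlation.

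The Synopsis and Section 9.5.7 both state that "missing values for endpoints analyzed via generalized estimating equations will not be directly imputed", and the justification is "the assumption that the model specification is correct and the data is missing completely at random" (MCAR). For continuous endpoints fitted by likelihood, the same paragraph needs only missing at random (MAR). Sensitivity analyses are optional, and further detail is left to a SAP that "will be written following finalization of the protocol and prior to the interim analysis of the Part A data" (Section 9.5). The SAP's missing-data rules are not in the supplied text.

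On stopping, Section 6.7.2.1 says "the subject may be discontinued for the following reasons", and its list includes lack of efficacy and adverse events. Women withdrawn from treatment are to "continue daily eDiary recording up to Week 36 visit in order to continue to collect efficacy data", but only where this is appropriate. The next section, "Follow-up for discontinued subjects" (6.7.2.2), is marked not applicable. For women who leave the study, Section 6.7.2 says: "Subjects discontinuing participation in the study between Day 1 and Week 24 visits should undergo the procedures required at Week 24 visit".

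**The concern.** MCAR requires that missingness be unrelated even to pain response already recorded. Stopping for lack of efficacy breaks that almost by definition, and stopping for adverse events may differ by dose and by response. The primary endpoint therefore rests on a stricter assumption than the continuous analyses of the same diary scores.

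Diary continuation reduces the problem without removing it. It is conditional, the following section appears to say something different, and closing-visit procedures cannot supply the daily scores behind a 4-week mean. A woman who leaves, or stops the diary, before the last 4-week window has no week-12 outcome.

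If stopping depends on earlier response and does so differently by arm, the responder rates and the dose-versus-placebo differences are biased. Section 9.6.1 gives these Part A results to the sponsor for planning later studies.

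**Working it through.** **The plan's own figure.** Section 9.2 assumes 45.5% v 76.9%, two-sided alpha 0.05, 90% power, 55 per arm. With mean rate 0.612 and difference 0.314:

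- Uncorrected: n = [1.960·√(2·0.612·0.388) + 1.282·√(0.455·0.545 + 0.769·0.231)]² / 0.314² = 48.5, so 49.
- Continuity-corrected: n = (48.5/4)·[1 + √(1 + 4/(48.5·0.314))]² = 54.7, so 55.

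The stated 55 is reproduced. Fisher exact power at 55 is 90.2%; the uncorrected formula gives 93.3%. The figure contains no dropout allowance, and no dropout rate is given anywhere.

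**Set-up (assumptions).** Latent normal scores at weeks 4, 8 and 12, correlation 0.7, cut to give 45.5% (placebo) or 76.9% (active) responders. Stopping after weeks 4 and 8 depends on response in that period. A share of stoppers (0%, 50%, 75%) keeps the diary. There were 400,000 subjects per arm per scenario. With a saturated arm-by-period model and independence working correlation, the GEE estimate equals the observed week-12 proportion, so that is what was computed. Baseline was not modelled.

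**Estimated difference in points (true value 76.9 − 45.5 = 31.4).** Risks are per 4 weeks, responders/non-responders.

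| Pattern | Placebo | Active | 0% keep diary | 50% | 75% |
|---|---|---|---|---|---|
| Opposite patterns | 3%/20% | 12%/8% | 25.8 | 28.9 | 30.5 |
| Placebo lack of efficacy only | 3%/15% | 5%/5% | 28.3 | 29.9 | 30.6 |
| Inflating | 15%/3% | 3%/20% | 37.5 | 34.1 | 32.8 |
| Same risks in both arms | 3%/15% | 3%/15% | 30.1 | 30.7 | 31.1 |
| Dose only | 5%/5% | 12%/12% | 31.4 | 31.5 | 31.6 |

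Repeat runs agreed to within about 0.3 points. In all these cases multiple imputation under MAR gave 31.2 to 31.6, and GEE with a well-matched exchangeable correlation gave 31.1 to 31.8.

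**How the bias arises, no diary continuation.**

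- Opposite patterns: 22.8% (placebo) and 20.8% (active) are missing. Observed rates are 50.3% and 76.2%, errors of +4.8 and −0.7 points. The odds ratio is 3.15 against a true 4.0.
- Inflating: 16.2% and 13.1% are missing. Observed rates are 42.4% and 79.9%, errors of −3.1 and +3.0. The odds ratio is 5.41.
- Dose only: treatment is in the model, so stopping that depends on arm alone causes no bias.

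**At 55 per arm** (opposite patterns, 700 runs, 20 imputations, Rubin's rules; full-data power about 93%):

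| Keep diary | Method | Difference | Power | Coverage |
|---|---|---|---|---|
| 0% | Independence GEE | 26.1 | 69.1% | 92.1% |
| 0% | Imputation | 31.2 | 89.7% | 96.6% |
| 50% | Independence GEE | 28.7 | 84.6% | 94.7% |
| 50% | Imputation | 31.0 | 92.6% | 97.0% |

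**A second set of assumptions.** Correlation was 0.5 or 0.7, week 4/8 response 35%/42% on placebo and 60%/70% on active, dropout about 8% to 30%, 1,000 runs.

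- With the same response-dependent rule in both arms, observed-case bias was −0.2 to −1.7 points.
- Imputation had 0.6 to 5.4 points more power than observed cases in every scenario. Inverse-probability weighting ranged from 1.2 points less to 0.6 more.

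A separate null case used correlation 0.6, true rates of 45.5% in both arms and non-responder stopping concentrated in the active arm. Independence GEE showed a spurious +4.8 points and rejected in 7.7% of 300 runs (standard error about 1.5 points, so indicative only). Exchangeable GEE gave −0.6 points and 4.0%.

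**Why non-responder imputation should not be primary.** Dose only, no continuation: 0.88² × 76.9 − 0.95² × 45.5 = 59.6 − 41.1 = 18.5 points, against a true 31.4.

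**The case against.** The case for leaving the plan nearly as it is has real force.

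- *The largest errors assume that no stopper keeps the diary, which the protocol works against.* True. In the placebo lack-of-efficacy case with 50% or 75% continuing, the bias is 1.5 or 0.8 points. The standard error of the difference at 55 per arm is √(0.455·0.545/55 + 0.769·0.231/55) = 8.8 points, so this is under 0.2 standard errors. Even opposite patterns with half continuing keep 94.7% coverage.
- *Independence correlation is an assumption, and a suitable exchangeable structure nearly removes the bias.* Also true, but the plan names no structure, and choosing one does not make GEE formally valid under MAR.
- *The stopping patterns are speculative, the inflating one especially: it has placebo responders leaving most often.* Fair as to that pattern. Overstatement does not depend on it, though: the null case needs only non-responders leaving the active arm more often.
- *The simulation omits baseline, and imputation is flattered by a correctly specified model.* Both stand. The power gain is a best case for a bounded 0–3 diary mean.
- *Section 9.5.2 divides by non-missing days, so a woman leaving during weeks 9 to 12 may still have a score.* Correct. The problem concerns those lost before that window.
- *Details are deferred to the SAP, the study is exploratory, and a mixed model of mean VRS offers an MAR cross-check.* The SAP may already specify a better method. But the protocol itself fixes MCAR without imputation, and the cross-check does not correct the responder estimate.
- *Section 6.7.2.2 may only mean nothing beyond what 6.7.2 and 6.7.2.1 require.* Possible, but the text should say so.

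These points limit size and priority. They do not supply a reason to prefer MCAR.

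**Conclusion.** The concern holds. The protocol commits its primary endpoint to an assumption that its own stopping criteria make doubtful, when a weaker assumption is available from the same data.

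Size and direction are unknown because no dropout rate is given. Under the assumed risks with independence correlation, the bias runs from −5.6 to +6.1 points with no diary continuation (about 0.6 to 0.7 standard errors in the worst cases) and from −2.5 to +2.7 with half continuing. It is about a point or less when both arms share the 3%/15% rule, and essentially nil when stopping depends on dose alone. A well-matched working correlation would also remove most of it. The change should be made because it is cheap and the results guide later studies; the trial does not fail without it. Confidence is medium.

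**What to change.** Before the unblinded Part A analysis:

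1. Replace the MCAR, no-imputation rule for the primary endpoint with an MAR-valid method. For example, multiply impute the continuous 4-week mean VRS from arm, baseline and earlier 4-week means, derive responder status, fit the planned GEE, and combine by Rubin's rules. Weighted GEE is an acceptable alternative.
2. Use diary data recorded after treatment withdrawal, and name the working correlation.
3. Make a sensitivity analysis mandatory: count missing week-12 outcomes as non-response, labelled as a stress test and not as the main estimate.
4. Reconcile 6.7.2.1 with 6.7.2.2.
5. If the SAP already specifies an MAR method, align Section 9.5.7 and the Synopsis with it.

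The cost is wording in Section 9.5.7, the Synopsis and the SAP, plus modest programming; no new data or subjects. The downside is that an imputation or weighting model must be specified and could be wrong, and intervals may widen slightly. In these runs they did not: the mean width for the log odds ratio was 1.79 with imputation against 1.86.
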